6.6 Interim Analyses and Data Monitoring

A study team and SMC safety and PK review will occur after Part A; 6 participants in Group 2 (severe renal impairment and ESRD, not on dialysis) and 6 participants in Group 1A, their matched controls, are enrolled and complete follow-up through Day 12 (Visit 02). This review will decide if Part B will be conducted and whether enrollment for Group 3 (eGFR 60-89), and Group 4 (eGFR 30-59) will occur. The interim safety and PK review will present data by group, including AEs, SAEs, clinical laboratory tests, vital signs and 12-lead ECG, and PK analysis of pretomanid. Cumulative data for all participants enrolled will be included in the safety and PK reviews. The interim safety and PK reviews will not include any statistical hypothesis testing.

6.7 Multicenter Studies

This study is planned to be conducted at multiple sites; however, data will be pooled across all clinical sites for analysis with the exception of demographics summaries and PK summaries that may be presented both overall and by site.

6.8 Multiple Comparisons/Multiplicity

While multiple PK parameters will be estimated in two sources, plasma and urine, no hypothesis testing will be performed. Summary statistics and confidence intervals will be used rather than formal hypothesis testing.

7 STUDY PARTICIPANTS

7.1 Disposition of Participants

Participant disposition in the study will be tabulated by renal impairment group in [Table 7](#). This table will show the total number of participants screened, enrolled, that received treatment, completed all PK blood draws, terminated early, that were replaced, and included in analysis. This table will be stratified by renal impairment group and presented overall.

[Table 10](#) will present a summary of the reasons that participants were screened but not enrolled.

The composition of analysis populations, including reasons for participant exclusion, by renal impairment group, will be presented in [Table 8](#).

A flowchart showing the disposition of participants, adapted from the consort statement, will be included ([Figure 1](#)). This figure will depict the number of participants screened, enrolled, terminating early, and included in analysis, stratified by renal impairment group.

A listing of participant disposition including the protocol version at time of screening will also be included ([Listing 2](#)) as well as a listing of participants that terminated the study early and the reason for termination ([Listing 3](#)).

7.2 Protocol Deviations

A summary of participant-specific protocol deviations will be presented by the reason for the deviation, the deviation category, and renal impairment group for all participants ([Table 4](#)), as well as similar summaries for major participant-specific protocol deviations that may affect analyses. All participant-specific protocol deviations and non-participant specific protocol deviations will be included as data listings in [Appendix 3](#) ([Listing 4](#) and [Listing 5](#), respectively).

8 EFFICACY EVALUATION

This is PK study and does not include any efficacy analysis.

8.1 Primary Efficacy Analysis

Not applicable.

8.2 Secondary Efficacy Analyses

Not applicable.

8.3 Exploratory Efficacy Analyses

Not applicable.

9 SAFETY EVALUATION

All summaries and analysis of safety data will be presented for the Safety Analysis Population. Safety summaries will be presented by renal impairment group and overall.

9.1 Demographic and Other Baseline Characteristics

Listings will be sorted by renal impairment group, participant ID, parameter (if applicable), and visit (if applicable). Continuous variables will be summarized using the following descriptive statistics: n (non-missing sample size), mean, standard deviation, median, maximum and minimum. All categorical measures will be summarized by the frequency and percentages (based on the non-missing sample size) of observed levels. The denominator for the percentages may be based on the number of non-missing observations for an assessment or based on the number of participants in a population. This will be described for each table and clarified in footnotes as needed.

Summaries of age, height, weight (measured at baseline), BMI (measured at baseline), sex, ethnicity, and race will be presented by renal impairment group and overall ([Table 13](#); [Table 14](#)) as well as by site ([Table 11](#) and [Table 12](#)). Ethnicity is categorized as Hispanic or Latino, not Hispanic and not Latino, Not Reported, or Unknown. In accordance with NIH reporting policy, participants may self-designate as belonging to more than one race or may refuse to identify a race, the latter reflected in the electronic Case Report Forms (eCRF) as “No” to each racial option.

Individual participant listings ([Appendix 3](#)) will be presented for all demographics ([Listing 7](#)).

9.1.1 Prior and Concurrent Medical Conditions

Complete medical history will be obtained by interview of participants at the screening visit and will be reviewed and updated upon admission on Day -1, again on Day 1 prior to dosing, and again on Days 4, 5 and 12 ± 2 . The medical history will also be reviewed and updated at any early termination visit. Participants will be queried regarding a history of medical disorders or procedures performed on the head, eyes, ears, nose, throat as well as blood and lymphatic, cardiovascular, endocrine and metabolic, respiratory, musculoskeletal, gastrointestinal, genital and reproductive, and hepatobiliary and pancreas systems. Participants will also be solicited for any medical history of cancer, immunodeficiency, psychiatric, drug or alcohol dependence, dermatologic, autoimmune disease, urologic, allergies, and neurologic conditions as well as any other significant medical history including conditions, diagnoses, or procedures.

All current illnesses and pre-existing medical conditions will be MedDRA® coded using MedDRA dictionary version 27.0 or higher. Summaries of participants' pre-existing and newly developed medical conditions will be presented by status (i.e. pre-existing or newly developed), renal impairment group, System Organ Class (SOC) and Preferred Term (PT) as appropriate ([Table 15](#) through [Table 18](#)).

Individual participant listings will be presented for all medical conditions ([Listing 8](#)).

9.1.2 Prior and Concomitant Medications

Summaries of medications that were started prior to dosing and continuing at the time of dosing or initiated after dosing will be presented by WHO Drug at the Anatomical Therapeutic Chemical (ATC) Levels 2 and 3 and renal impairment group ([Table 78](#)). Individual participant listings will be presented for all concomitant medications ([Listing 15](#)).

9.2 Measurements of Treatment Compliance

Details of the date and time of the pre-dose meal beginning and ending as well as study product administration will be collected. Dates of dose administered will be presented by Site and Impairment Group ([Table 9](#)). Any participant enrolled but not dosed will be presented in the participant disposition table ([Table 7](#)).

9.3 Adverse Events

An AE is defined as any untoward medical occurrence in a clinical study participant administered a medicinal product, which does not necessarily have a causal relationship with this treatment. An AE can therefore be any unfavorable or unintended sign (including an abnormal laboratory finding), symptom, or disease temporally associated with the use of a medicinal (investigational) product, whether or not it is related to the medicinal (investigational) product. This includes exacerbation of a pre-existing condition or events, intercurrent illnesses, drug interaction or the significant worsening of the indication under investigation that is not recorded elsewhere in the eCRF under specific efficacy assessments. Anticipated fluctuations of pre-existing conditions, including the condition under study, that do not represent a clinically significant exacerbation or worsening need not be considered AEs.

It is the responsibility of the Investigator to document all AEs that occur during the study. AEs must be reported on the appropriate page(s) of the eCRF. All AEs will be coded using the MedDRA dictionary Version 27.0 or higher.

TEAEs are defined as any event that occurs or worsens on or after the day that study treatment initiated. AEs recorded in the eCRF which began prior to treatment will not be included in the summary tables but will be included in the AE data listings ([Listing 9](#)).

The severity of AEs will be graded according to National Cancer Institute (NCI) Common Terminology Criteria for Adverse Events (CTCAE) Version 5.0. The severity of the AE should be the maximum over the course of the AE. For AEs not listed in the NCI CTCAE, the Investigator should determine the severity of the AE according to the following criteria, as described in Section 8.1.1.1 of the protocol.

- Mild (Grade 1): Asymptomatic or mild symptoms, Events require minimal or no treatment and do not interfere with the participant's daily activities.
- Moderate (Grade 2): Events result in a low level of inconvenience or concern with therapeutic measures. Moderate events may cause some interference with functioning and daily activities.
- Severe (Grade 3): Severe or medically significant but not immediately life threatening, interrupt the participant's daily activities; and may require intervention and hospitalization. Severe events are usually incapacitating.
- Life-threatening (Grade 4): Life-threatening consequences; urgent intervention indicated.

AEs characterized as intermittent require documentation of onset and duration of each episode.

The causal relationship between the study drug and an AE will be assessed by a delegated, licensed study clinician listed on the Form FDA 1572. All AEs will be deemed related to study drug unless explicitly assessed as not related. Only two categories will be used to describe the relationship between study drug and an AE, related and not related. Any AEs for which a relationship is not provided will be assumed to be related. To assist the assessor in determining the relationship the following guidelines are provided in Section 8.1.1.1 of the protocol.

- Related – There is a reasonable possibility that the study product caused the AE. Reasonable possibility means that there is evidence to suggest a causal relationship between the study product and the AE.
- Not Related – There is not a reasonable possibility that the administration of the study product caused the event

Adverse Events will be reported using the Safety Population.

9.3.1 Solicited Events and Symptoms

There are no solicited events to be captured for this study.

9.3.2 Unsolicited Adverse Events

An overall summary of AEs will be presented ([Table 19](#)) that includes the number of events and the number and percentage of participants who experienced at least one AE or TEAE, by renal impairment group. This summary will also include treatment-related TEAEs, SAEs, and TEAEs leading to early termination. AEs will be summarized using discrete summary statistics and presented at the participant level. TEAEs will also be summarized ([Table 21](#) through [Table 24](#)) by renal impairment group in a separate table at the event level by MedDRA SOC and PT. If a participant reports the same PT multiple times within the same SOC, that PT will only be reported once within that SOC. As with the PT, if a participant reports multiple conditions within the same SOC, that SOC will only be reported once at the SOC summary level. SOCs will be reported in ascending alphabetical order, PTs will be listed in order of descending frequency for all participants included in the table within each SOC.

TEAEs that occur in 5% of participants in any impairment group will be presented ([Table 20](#)) by SOC, PT and impairment group.

A summary of TEAEs by maximum severity will be presented ([Table 25](#)). The number of participants within any TEAEs (along with percentages) will be tabulated by SOC and PT within each SOC by renal impairment group. To count the number of participants within any TEAEs, if a participant has multiple TEAEs coded to the same PT within the same SOC, the participant will be counted once under that maximum severity.

Summaries of related TEAEs will be presented ([Table 26](#) through [Table 29](#)) by impairment group, SOC, and PT.

The denominator for all percentages will be the number of participants being summarized.

A bar chart of serious and non-serious related TEAEs by SOC will also be presented ([Figure 2](#) and [Figure 3](#))

All AEs will be listed ([Listing 9](#)). All SAEs will also be listed separately ([Table 30](#)). Non-serious, moderate or severe adverse events will be listed ([Table 31](#)). Other significant adverse events will also be listed ([Table 32](#)).

9.4 Deaths, Serious Adverse Events, and other Significant Adverse Events

SAEs will be listed in [Table 30](#) and will include participant ID, renal impairment group, AE Description, Reason Reported as an SAE, Relationship to Study Treatment, Alternate Etiology if Not Related, Outcome, and Duration of Event (in days).

9.5 Pregnancies

Pregnancy is not considered an adverse event; however, for females, information will be collected for any pregnancies which occur during study drug administration until the Study Day 85 Visit. Male participants should notify the study team if a pregnancy occurs in a partner during the study after study drug administration. If the male participant reports a pregnancy, information about the outcome of pregnancy in the female partner of male participant will be handled through contact with the male participant. Certain pregnancy outcomes (congenital anomaly or birth defect in an offspring of a participant taking study drug) will require submission as an SAE. Listings summarizing the total pregnancies, number of live births, and number of spontaneous abortions, elective abortions or still births and listing of pregnancies and outcomes will be presented ([Listing 17](#), [Listing 18](#), [Listing 19](#), [Listing 20](#), and [Listing 21](#)).

9.6 Clinical Laboratory Evaluations

Clinical safety laboratory adverse events will be collected prior to study product administration during the screening visit (Visit 00A), on Day 5 (Visit 01N), and on Day 12 (Visit 02). Clinical laboratory parameters to be evaluated will include hemoglobin (Hgb), alanine aminotransferase (ALT), aspartate aminotransferase (AST), total bilirubin, blood urea nitrogen (BUN), serum creatinine (including eGFR), serum potassium, and serum magnesium. At only Visit 00A human immunodeficiency virus (HIV), hepatitis B surface antigen (HBsAg), and hepatitis C virus (HCV) will also be obtained and presented in [Listing 12](#). Screening laboratory assessments may be repeated once per investigator discretion.

Urine pregnancy tests will be performed locally on all women of childbearing potential by the local site laboratory at second screening (Visit 00B), on the day of hospital admission (Visit 00C), prior to administration of study product (Visit 01A), on Day 12 (Visit 02), and any Early Termination (ET). Results must be negative and known prior to administration of study product. Urine drug screen and alcohol screen will also be done at Visit 00B and 00C for all participants.

The number and percentage of participants with at least one clinical safety laboratory finding assessed as of mild or greater severity through Day 12 is presented in the overall summary of adverse events ([Table 19](#)).

The distribution of chemistry laboratory results by severity, time point, and renal impairment group will be presented beginning at [Table 35](#) and concluding at [Table 52](#). The distribution of hematology results by severity, time point, and renal impairment group will be presented in [Table 68](#) and [Table 69](#). Descriptive statistics including mean, standard deviation, median, minimum and maximum values and change from baseline by time point, for each chemistry laboratory parameter, will be summarized in [Table 53](#) and concluding at [Table 60](#). Descriptive statistics including mean, standard deviation, median, minimum and maximum values and change from baseline by time point, for each hematology laboratory parameter, will be summarized in [Table 70](#). Shift tables will be presented for each chemistry laboratory parameter beginning at [Table 61](#) and concluding at [Table 67](#). Shift tables will be presented for each hematology laboratory parameter in [Table 71](#). Change from baseline plots for continuous chemistry laboratory parameters will also be presented beginning at [Figure 4](#) and concluding with [Figure 19](#). Change from baseline plots for continuous hematology laboratory parameters will also be presented in [Figure 20](#) and [Figure 21](#).

[Listing 10](#) will provide a complete listing of individual chemistry laboratory results with applicable reference ranges. [Listing 11](#) will provide a complete listing of individual hematology laboratory results with applicable reference ranges. [Table 33](#) will provide a listing of abnormal chemistry laboratory values. [Table 34](#) will provide a listing of abnormal hematology laboratory values.

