18. Use of St. John's Wort within 7 days prior to admission and during the entire study.
19. Consumption of products containing grapefruit within 5 days prior to dosing until Visit 01N.
20. Donation of whole blood or blood products >500 mL within 30 days from screening and/or plans to donate during the study or up to 14 days after dosing.
21. Participation in another interventional clinical trial within 30 days prior to dosing until after the last study visit.
22. Hgb <8.0 g/dL in both men and women at the screening visit.
23. Positive Screening test for hepatitis C virus (HCV), hepatitis B virus (HBV), or HIV.
24. Renal transplant.
25. Scheduled for hemodialysis or peritoneal dialysis.
26. Presence of any condition or finding⁵ which would jeopardize participant safety, impact study result validity, or diminish the participant's ability to undergo all study procedures and assessments.

⁵In the opinion of the investigator

27. For men, semen donation for the duration of the study.
28. AST and ALT > 2.5 x upper limit of normal (ULN).
29. Hyperbilirubinemia >1.5 x ULN.

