8.1.1 Adverse Events

Adverse Event (AE): The International Council for Harmonisation (ICH) E6 defines an AE as any untoward medical occurrence in a patient or clinical investigation participant administered a pharmaceutical product regardless of its causal relationship to the study treatment. The FDA defines an AE as any untoward medical occurrence associated with the use of a drug in humans, whether or not considered drug related.

An AE can therefore be any unfavorable and unintended sign (including an abnormal laboratory finding), symptom, or disease temporally associated with the use of a medicinal (investigational) product. The occurrence of an AE may come to the attention of study personnel during study visits and interviews of a study participants presenting for medical care, or upon review by a study monitor.

All AEs, systemic (participative and quantitative) reactions from Day 1 to the end of the study, will be captured on the appropriate (source documentation and eCRF) ([Section 8.3](#)). Information to be collected for AEs includes event description, date of onset, assessment of severity, relationship to study product and alternate etiology (assessed only by those with the training and authority to make a diagnosis and listed on the Form FDA 1572 as an investigator), date of resolution, seriousness, and outcome. AEs occurring during the trial collection and reporting period will be documented appropriately regardless of relationship to the study product. AEs will be followed through resolution or until stable.

Any medical condition(s) that is/are present at the time that the participant is screened will be considered as baseline and not reported as an AE but must be reported in the medical history

(APPENDIX A: Schedule of Study Procedures and Evaluations). However, if the severity of any pre-existing medical condition increases, it will be recorded as an AE (Section 8.3).

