3.3 Study Definitions and Derived Variables

Baseline will be defined as the last recorded value prior to drug administration.

An AE is any unfavorable and unintended sign (including an abnormal laboratory finding), symptom, or disease temporally associated with the use of a medicinal (investigational) product.

A Treatment Emergent Adverse Event (TEAE) is any new or worsening AE or pre-existing condition that worsens after study drug administration.

A Serious Adverse Event (SAE) is an AE or suspected adverse reaction that, in the view of either the site principal investigator (PI) or sponsor, results in any of the following outcomes:

- Death
- Life-threatening
- Inpatient hospitalization or prolongation of existing hospitalization
- Persistent or significant incapacity or substantial disruption of the ability to perform normal life functions
- A congenital anomaly/birth defect, or

- Any medical event that based upon appropriate medical judgement may jeopardize the health or safety of the patient or participant and may require medical or surgical intervention to prevent one of the other listed outcomes.

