14.3 Safety Data

14.3.1 Displays of Adverse Events

Table 16: Overall Summary of Adverse Events

	Mild Renal Impairment (N = x)		Moderate Renal Impairment (N = x)		...		All Participants (N = x)	
	n	%	n	%	n	%	n	%
Participants ^a with								
At least one lab finding of mild or worse severity through Day 12	x	x	x	x	x	x	x	x
At least one unsolicited adverse event	x	x	x	x	x	x	x	x
At least one unsolicited treatment emergent adverse event	x	x	x	x	x	x	x	x
At least one related unsolicited treatment emergent adverse event	x	x	x	x	x	x	x	x
Mild (Grade 1)	x	x	x	x	x	x	x	x
Moderate (Grade 2)	x	x	x	x	x	x	x	x
Severe (Grade 3)	x	x	x	x	x	x	x	x
Not yet assessed								
At least one severe (Grade 3) unsolicited treatment emergent adverse event	x	x	x	x	x	x	x	x
Related	x	x	x	x	x	x	x	x
Unrelated	x	x	x	x	x	x	x	x
At least one treatment emergent serious adverse event ^b	x	x	x	x	x	x	x	x
At least one related treatment emergent serious adverse event	x	x	x	x	x	x	x	x
At least one treatment emergent adverse event leading to early termination ^c	x	x	x	x	x	x	x	x

N = Number of participants in the Safety Population

^a Participants are counted once for each category regardless of the number of events.

^b A listing of Serious Adverse Events is included in the Listing of Serious Adverse Events table.

^c As reported on the Adverse Event eCRF.

Table 17: Treatment Emergent Adverse Events Occurring in 5% of Participants in Any Impairment Group by MedDRA System Organ Class and Preferred Term, and Impairment Group - Safety Population

[Implementation Note: this table is used to complete the “Other Adverse Event Template” for clinicaltrials.gov reporting (See slide 6 in <https://prsinfo.clinicaltrials.gov/trainTrainer/Adverse-Events-Module.pdf>). Threshold value may be 0% to 5% (default 5). This table should include a row for All PT/SOC and for any PT/SOC reported by \geq [threshold] % participants in any group. Note, this table summarize SAEs and non-serious events separately. This includes all adverse events collected (e.g., solicited, unsolicited, AESI, laboratory adverse events, etc.), regardless of relationship to study product, so this summary should combine data collected across multiple eCRFs/domains.]

Preferred Term	MedDRA System Organ Class	Mild Renal Impairment (N=X)			Moderate Renal Impairment (N=X)			...			All Participants (N=X)		
		n	%	Events	n	%	Events	n	%	Events	n	%	Events
Serious Adverse Events													
All	All	x	x	x	x	x	x	x	x	x	x	x	x
PT1	SOC1	x	x	x	x	x	x	x	x	x	x	x	x

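### The overall adverse event table counts any graded laboratory finding through Day 12, new or not, so Group 2 participants are counted because of their entry eGFR

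*SAP*

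**What the plan says.** SAP 9.6 (Clinical Laboratory Evaluations) says that the overall summary of adverse events will show the number and percentage of participants with "at least one clinical safety laboratory finding assessed as of mild or greater severity through Day 12". The shell of that table (Table 16 in SAP Appendix 1, cited as Table 19 in the text of 9.6) has the matching first row: "At least one lab finding of mild or worse severity through Day 12". Neither place gives a start point or a comparison with baseline. SAP 9.6 lists the screening visit, Day 5 and Day 12 as the laboratory collection times.

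Other rows of the same shell do carry a baseline condition, for example "At least one unsolicited treatment emergent adverse event". SAP 3.3 defines such an event as "any new or worsening AE or pre-existing condition that worsens after study drug administration". Protocol 8.1.1 says that a medical condition present at screening "will be considered as baseline and not reported as an AE", unless its severity increases.

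Protocol 8.1 limits laboratory adverse events to those occurring from dosing through Visit 02 (Day 12). SAP 9.3 adds that "AEs recorded in the eCRF which began prior to treatment will not be included in the summary tables".

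**The concern.** The groups are defined by a laboratory value that the SAP also grades. Group 2 enters with eGFR below 30 mL/min and controls with 90 or above (SAP 3.3.2), and eGFR and creatinine each have severity tables in the shells. Other entry limits differ in the same direction. Renal participants are excluded only for "Hgb <8.0 g/dL in both men and women at the screening visit", while the control threshold is 10.0 g/dL. The bilirubin limit is 1.5 x ULN for renal groups and ULN for controls, and the AST/ALT limits are 2.5 x ULN and ULN.

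A row that counts any graded value therefore mixes what participants brought into the trial with what followed the dose. A reader of the overall table could take an excess in the renal column for a laboratory effect of pretomanid, and nothing in the table would show that it preceded dosing.

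**Working it through.** The documents state no figure for this row, so there is none to reproduce. The check compares the rules and then works through an illustration.

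**Step 1: the rules side by side.**

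| Place | Post-dose start? | New or worse required? | Covers graded laboratory findings? |
|---|---|---|---|
| SAP 9.6 and shell Table 16, laboratory row | no | no | yes |
| SAP 3.3, treatment-emergent definition | yes | yes | only if recorded as an adverse event |
| SAP 9.3, exclusion from summary tables | yes | no | only adverse events recorded in the eCRF |
| Protocol 8.1, laboratory adverse events | yes | no | yes, as adverse events |

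Reading Protocol 8.1 into the row supplies the start point and so removes the screening sample. It does not remove a stable abnormality found again on Day 5 or Day 12.

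**Step 2: entry eGFR alone, no drug effect.** Inputs are the eGFR ranges in SAP 3.3.2 and the group sizes in Table 1. The grading scale is CTCAE v5.0, whose cut-offs the documents do not print, so the Grade 1 cut-off is an assumption. A group is counted in full if its whole entry range lies below the cut-off. Under the post-dose reading this also assumes that eGFR stays on the same side of the cut-off.

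| Assumed Grade 1 cut-off (mL/min) | Group 2, below 30 | Group 4, 30-59 | Group 3, 60-89 | Controls, 90 or above |
|---|---|---|---|---|
| below 90 | 6/6 | 6/6 | 6/6 | 0/18 |
| below 60 | 6/6 | 6/6 | 0/6 | 0/18 |
| below 30 | 6/6 | 0/6 | 0/6 | 0/18 |

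In Part A alone the control figure is 0/6.

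**Step 3: all laboratory parameters.** Let p be the share of a group with a graded value before dosing that persists. Let q be the chance of a new or worse finding, taken as independent of p and equal in both groups.

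- Row as written: 1 - (1 - p)(1 - q)
- Difference between groups: (p_renal - p_control)(1 - q)
- New-or-worse row: q in both groups, so the difference is 0

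| p renal | p control | q | Renal | Control | Difference (points) |
|---|---|---|---|---|---|
| 1 | 0 | 0 | 100% | 0% | 100 |
| 1 | 0 | 0.10 | 100% | 10% | 90 |
| 1 | 0.20 | 0.10 | 100% | 28% | 72 |
| 0.50 | 0.10 | 0.10 | 55% | 19% | 36 |

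For the third line, the control figure is 1 - 0.80 x 0.90 = 0.28. In the last three lines a new-or-worse row would show 10% in both groups. The values of p and q are illustrative.

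**The case against.** The strongest reply is that the row can be read with the protocol. SAP 9.6 calls these results laboratory adverse events, the table is a summary of adverse events, Protocol 8.1 starts the window at dosing, and Protocol 8.1.1 does not treat a screening condition as an adverse event unless it worsens. On that reading the row could already mean new or worse. This stands only in part. The protocol does supply a start point. But both the row and SAP 9.6 count findings by grade, not recorded adverse events, and the SAP 9.3 exclusion reaches only events recorded in the eCRF. A programmer who follows the shell would apply no worsening condition.

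The second reply is that no information is lost, and this stands. Shell Table 32 gives any-chemistry grades by group at baseline and as the post-baseline maximum, Table 65 does so for hemoglobin, and shift tables cover most parameters (the shells have none for magnesium). The laboratory secondary outcome is mean change from baseline.

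A reader might go further and infer that the trial's main safety comparison is biased by about 100 points in every renal group. The documents do not support that:

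- The row is not one of the prespecified safety outcomes. Progress to Part B rests on pretomanid AUC with a safety review, and the halting rules use deaths, related SAEs and related events of Grade 3 or higher.
- For the moderate and mild groups the effect depends on cut-offs that are not printed, and those groups are enrolled only if Part B opens.
- A control count near zero follows for eGFR only. Controls may enter with hemoglobin just above 10 g/dL. Their exclusion list has no item for hyperkalemia or hypomagnesemia, and its transaminase item joins AST and ALT with *and*, so one raised enzyme is not clearly excluded.

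**Conclusion.** The point holds as a defect in one descriptive row. As written, the row counts all 6 Group 2 participants with no drug effect at each assumed eGFR cut-off of 30, 60 or 90 mL/min, against no control on eGFR alone. This rests on eGFR being graded on a scale whose Grade 1 cut-off is at least 30, and on stable values after dosing. Group 2 is enrolled in Part A, so the effect does not depend on Part B. Once other parameters are counted the gap shrinks as more controls have graded values, so 100 percentage points is an upper bound. The row should be changed because it misleads where the overall safety picture is read first, but no endpoint, decision rule or data item is compromised.

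**What to change.** Change SAP 9.6 and the shell row to: *at least one post-dose laboratory finding that is new or at least one grade worse than the last pre-dose grade, through Day 12*. If a count of pre-existing abnormalities is wanted, give it as a separate row based on pre-dose grades only. The existing count should not be moved to the baseline table, because it includes Day 5 and Day 12 values and is not a baseline characteristic. Correct the table number cited in SAP 9.6 (19) to match the shell (16) in the same edit.

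The cost is a wording change and one derivation. Baseline grades are already needed for the severity and shift tables, and no extra data are collected.
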